### **B1. PURPOSE OF PROTOCOL**

The purpose of this study is to compare semen parameters with in vitro fertilization (IVF)/intracytoplasmic sperm injection (ICSI) when male factor infertility patients abstain from ejaculation more than 48 hours (routine care) or less than 24 hours. We hypothesize that total motile sperm will be improved with EA less than 24 hours. Information from this trial could allow us to optimize chances for a successful pregnancy in patients who need IVF/ICSI.

### **B2. SIGNIFICANCE AND BACKGROUND FOR THE STUDY**

The semen analysis is currently one of the main tests in diagnosing male factor infertility but does not measure fertilization potential (1,2). There are numerous parameters in a semen analysis that are affected by different factors with one being ejaculatory abstinence (EA) prior to artificial reproductive technology (ART). Current guidelines from the World Health Organization (WHO) recommend between 2 to 7 days of EA while the European Society of Human Reproduction and Embryology advises 3 to 4 days of EA prior to a semen sample (3,4). This EA period has been utilized for diagnostic purposes and was inherited in IVF/ICSI treatment procedures with minimal investigation.

Two prior studies showed optimal semen parameters when following the current WHO guidelines on EA (5,6). Conversely, other studies suggest shorter EA periods may provide benefit on certain semen parameters (7–13). Furthermore, a shorter EA may result in a reduced exposure to reactive oxygen species which leads to improved sperm quality (14,15). ROS may be a contributory factor to a male's infertility (16).

Two prior systematic reviews evaluated EA periods and correlations to semen quality in fertile and infertile males (17,18). Ayad et al reported despite the varied quality of studies, there may be enough evidence to favor a shorter EA period and guidelines should be revisited (17). Hanson et al reported that certain semen parameters improved with longer or shorter EA periods and no clear recommendations could be given (18). Both of these systematic reviews demonstrated conflicting results when evaluating total motile sperm.

To our knowledge, this is the first randomized control trial to evaluate semen parameters with varying EA periods in male factor infertility patients when IVF/ICSI is utilized for first time IVF patients. In addition, we will survey patients' ejaculatory mode and frequency during the IVF cycle. This will provide useful and practical information for physicians and patients when determining how to optimize chances for a successful pregnancy.

### **B3. DESCRIPTION OF RESEARCH PROTOCOL**

A. Study Design – Overview, Methods, Procedures

#### Overview

This will be a randomized controlled trial to compare semen parameters following EA for either more than 48 hours (routine care) or less than 24 hours among male factor infertility patients who receive IVF/ICSI.

#### Methods

Study participation will not influence any element of IVF treatment and all patients will be receiving the standard of care at Boston IVF. For participants who meet eligibility criteria and provide informed verbal consent, baseline demographic data will be obtained from their medical record including for example; age, race, education level, height, weight, baseline semen analysis, testosterone level, follicle stimulating hormone (FSH) level. Demographic data on the female partner will include parameters such as: age, race, education level, height, weight, gravidity, parity, anti-mullerian hormone (AMH) level, and day 3 FSH.

Eligible participants will have the study introduced by the medical care team. Eligible participants will be given information on study details (see study details for participants) as well as an ejaculatory calendar/survey (see survey and calendar) that can be used if the participant enrolls in the study (see study timeline). The medical care team will inform eligible participants that they will receive a recruitment email from the research team at [contact] followed by a phone call from the research team to see if eligible participants are willing to participate (see recruitment email). Eligible participants who meet inclusion and exclusion criteria whom do not get information regarding the study from the medical care team will also receive a recruitment email. If so, the research member will call the eligible participant to obtain verbal consent to enroll in the study (see verbal consent). If the participant does not answer, a voicemail will be recorded followed by a second phone call the following day. The recruitment email and verbal consent will occur between the pre-IVF period and before stimulation day 4 of the IVF cycle. If a participant consents to enrollment, we will make a note in the treatment plan for their cycle. Enrolled participants will receive a phone call from a member of the research team during stimulation day 6 to 8 to randomize the participant to EA > 48 hours (routine care) or EA < 24 hours (see randomization call). If the participant does not answer, a voicemail will be recorded followed by a second phone call the following day.

The semen sample provided on day of oocyte retrieval will be analyzed with a basic and advanced semen panel. Any remaining samples will be discarded per routine practice. Prior to providing the semen sample, participants turn in the completed survey/ejaculation history calendar to a member of the research team. Blank copies will be available for participants the day of egg retrieval if needed.

There is no clinical risk to your IVF cycle as the procedures followed are standard clinical practice. Study participation will not influence any element of the IVF treatment except for EA counseling. Currently there is no set protocol on how EA counseling is performed. Counseling on EA varies among the medical care teams at Boston IVF as some patients may or may not receive explicit EA instructions. Patients may be counseled by the medical care team with recommendations to abstain for > 48 hours at the time of their consult. All patients in this study are using ICSI to fertilize eggs and the number of sperm needed for treatment will not be compromised by ejaculatory abstinence < 24 hours. Participants who crossover to the alternate treatment arm will continue their participation in the study so that we can collect cycle outcome data. IVF stimulation protocols will be according to standard practice. ICSI and embryology practice will follow standard practice. Selection of embryos will be based on the current embryology laboratory selection protocols or by preimplantation genetic testing for aneuploidy (PGT-A). The number of embryos transferred will be based on the usual American Society of Reproductive Medicine guidelines. Any unused embryos will be disposed of or cryopreserved per

standard clinical protocols.

Outcomes

*Primary:* Total motile sperm (motility x concentration x volume)

# Secondary:

Clinical data from the IVF cycle randomized to intervention or control condition, will include but not be limited to the following: fertilization rate; blastocyst rate; number of morphologically normal blastocysts; number of euploid and aneuploid embryos (if preimplantation genetic testing-aneuploidy [PGT-A] performed); number of embryos transferred; implantation rate; biochemical pregnancy rate (defined as positive beta-hCG but no gestational sac visualized); clinical pregnancy rate (defined as confirmation of gestational sac on ultrasound); ongoing pregnancy rate (defined as confirmation of a gestational sac with at least one fetal pole with a fetal heartbeat); live birth rate (defined as delivery > 23 weeks gestation); Cumulative pregnancy rate; Miscarriage rate; Multiple pregnancy, defined as twins or higher-order gestations

Semen characteristics will be examined in relation to: Changes in semen analysis from baseline diagnostic sample An advanced semen analysis panel Time from last ejaculation to oocyte retrieval

All data that is collected for the trial is clinical data that would be collected and stored in the electronic medical record as part of routine clinical care. In addition to collecting outcome data from this initial IVF cycle, we will collect data regarding subsequent IVF cycles and outcomes for any of the frozen embryos created but not transferred in this cycle.

#### **Procedure**

Intervention

Participants will be randomized to EA more than 48 hours (routine care) or less than 24 hours from the day of their partner's oocyte retrieval.

# Randomization

We will use computer-generated block randomization in REDCap to randomize participants in a 1:1 ratio to the EA period more than 48 hours (routine care) or less than 24 hours. Randomization will be stratified by whether the patients receive PGT-A. Research staff will call participants on stimulation day 6 to 8 to notify participants which treatment arm they were randomized to. The participant can withdraw from the study at any time if desired or will have an opportunity to not continue with the treatment arm they were randomized to. We anticipate that most of the crossovers will occur due to participants wishing to be in the alternate EA period or not being able to produce a sample in the window assigned.

The purpose of this study is to examine semen parameters with IVF/ICSI when male factor infertility patients abstain from ejaculation more than 48 hours (routine care) or less than 24 hours. Information from this study would allow us to provide evidence-based recommendations to future patients who need IVF/ICSI.

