### **B. Statistical Considerations**

# **Sample Size Justification**

Our sample size calculation is based on data from Boston IVF from 2013 to 2018 for patients with less

than 3 million total motile sperm post prep for IVF/ICSI patients. The mean number of total motile sperm is 38 million  $\pm$  24 which will be our control group. We hypothesize that the mean number of total motile sperm at the time of retrieval will increase to 48 million. In order to achieve 80% power to detect the specified difference using a two-sided alpha of 0.05, we will need 90 evaluable participants per arm. We anticipate that approximately 15% of participants will drop out or crossover, and we will inflate the sample size by another 15% to account for a non-normal distribution. Thus, we aim to randomize 117 participants per arm for a total of 234 participants.

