# C. Subject Selection

### **Inclusion Criteria**

- Male Age 18 50 years and female age < 38 years
- First IVF cycle
- Abnormal semen parameters (at least 1 of the following on 2 semen analysis with at least one being in the past 12 months)
  - sperm concentration < 10 million/mL
  - unprocessed semen analysis with < 10 million motile sperm or processed semen analysis with < 3 million motile sperm
  - < 2 % normal forms (strict Kruger morphology)

- Female AMH > 0.7 and/or and day 2-4 FSH < 12

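### Allocation is stratified only on PGT-A and no baseline semen measure is prespecified in the primary analysis, so the plan gives up precision on total motile sperm

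*Combined protocol and SAP*

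**What the plan says.** On allocation, the Randomization section reads: "We will use computer-generated block randomization in REDCap to randomize participants in a 1:1 ratio". One stratifier is named: "Randomization will be stratified by whether the patients receive PGT-A". The Methods section describes PGT-A as one of the ways embryos are selected.

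The primary outcome is total motile sperm, the product of motility, concentration and volume. It is measured on retrieval day: "The semen sample provided on day of oocyte retrieval will be analyzed with a basic and advanced semen panel".

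On entry, a man needs "at least 1 of the following on 2 semen analysis with at least one being in the past 12 months". The options are a concentration below 10 million/mL, a motile count, or fewer than 2% normal forms. The motile-count option is itself an alternative: "unprocessed semen analysis with < 10 million motile sperm or processed semen analysis with < 3 million motile sperm".

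The Sample Size Justification uses Boston IVF data on men with fewer than 3 million motile sperm after preparation: "The mean number of total motile sperm is 38 million", with SD 24 million. The target is 48 million, with 90 evaluable and 117 randomized men per arm.

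The Methods section lists a baseline semen analysis among the data collected, and change from that sample appears among the secondary items. The Data Analysis section offers parametric or non-parametric tests, and log-binomial regression for risk ratios. It would assess confounders if randomization failed to balance them, but names no covariate, threshold or model for doing so.

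**The concern.** PGT-A is done on embryos, after the semen sample has been given, so it cannot change the primary outcome. Baseline sperm count is the natural predictor of that outcome, and the entry rule makes it vary widely. Only the unprocessed-count option caps motile sperm at 10 million. The concentration, morphology and processed-count options do not. As an illustration, 9 million/mL × 4 mL × 50% motile = 18 million. A man with fewer than 2% normal forms may have any count. The planning mean of 38 million is itself almost four times the cap.

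Two things are at stake. Variance that could be explained stays in the error term, so the interval is wider than it need be. And if more low-count men fall into one arm by chance, the unadjusted estimate moves, with no remedy fixed in advance.

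**Working it through.** **The plan's own figure.** With a difference of 10, SD 24, two-sided alpha 0.05 and 80% power, n per arm = 2 × (24 × (1.960 + 0.842) / 10)² = 90.4, which rounds up to 91. The stated 90 gives 79.8% power, so it reproduces to within rounding. The 117 is 90 × 1.30.

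**Standard error as planned.** SE = 24 × √(2/117) = 3.14 million with all 117 per arm analysed, and 24 × √(2/90) = 3.58 million with 90.

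**Severity as a component of that error.** The documents give neither the share of capped men nor their retrieval-day mean. I assume a share p of 10% or 30%, and a capped-group mean L of 10 or 20 million; the higher value allows for regression to the mean. The overall mean is taken as 38 million.

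- Gap between groups: g = (38 − pL)/(1 − p) − L
- SD of the chance shift in the arm difference at 117 per arm: g × √(2p(1 − p)/117)
- Share of planned variance: p(1 − p)g²/24²
- SE once severity group is conditioned on: 3.14 × √(1 − share)

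| p | L | g (million) | SD of shift | Share of variance | SE after conditioning |
|---|---|---|---|---|---|
| 10% | 20 | 20.0 | 0.78 | 6% | 3.04 |
| 10% | 10 | 31.1 | 1.22 | 15% | 2.89 |
| 30% | 20 | 25.7 | 1.54 | 24% | 2.73 |
| 30% | 10 | 40.0 | 2.40 | 58% | 2.03 |

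The shift is part of the 3.14 million and does not add to it. In the last row, (2.40/3.14)² = 0.58, which is the variance share again.

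Over a wider grid (20% to 50% capped, gaps of 10 to 40 million), the share runs from 3% to 69%. The 95% limits of the shift at 117 per arm run from ±1.0 to ±5.1 million.

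**Validity of the unadjusted test.** In 40,000 simulated trials with no treatment effect (30% capped, gap 30 million, 90 per arm), the overall type I error was 4.8%. An imbalance of 10 percentage points or more in capped men arose in 14% of trials, and among those the test rejected in 15%. Where the imbalance was under 5 points it rejected in 2.0%. The test is right on average but not conditionally on the imbalance that occurs.

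**Gain from a continuous baseline covariate.** Residual SD = 24 × √(1 − r²), where r is the assumed correlation between baseline and retrieval-day counts.

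| r | n per arm for 80% power | Power at 90 per arm |
|---|---|---|
| 0 | 91 | 79.8% |
| 0.3 | 83 | 83% |
| 0.5 | 68 | 90% |
| 0.7 | 47 | 97% |

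**The case against.** The strongest reply is that this is ordinary sampling error. If 24 million is the total SD, it already contains the differences between severity groups, so the test, interval and power calculation allow for them. That stands. A reader might infer that a shift of up to ±4.7 million (1.96 × 2.40) threatens a 10 million target over and above the planned error. The documents do not support that.

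PGT-A is also a reasonable stratifier for the secondary outcomes, which include euploid embryos, implantation, pregnancy and live birth. Using it does no harm to the primary outcome. The gap is that nothing prognostic for total motile sperm stands beside it.

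The Data Analysis section does provide for confounders. This is a partial safeguard, because the decision to adjust and the choice of covariates would follow sight of the data. The one regression it names, log-binomial, does not suit a continuous count.

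The gap between entry groups is also unknown. A reader might take it as established that it exceeds 10 million, but no figure in the documents shows this. The 38 million describes men with a low post-preparation count, not the whole eligible mix, and men entering on concentration may lie close to the capped group, as the 18 million illustration shows.

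Finally, a reader might infer that low-count men cannot be compared fairly without a severity stratum. Randomized subgroups are comparable in expectation either way. Their limit is size: at p = 10% there are about 12 such men per arm, and stratifying does not change that.

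**Conclusion.** The point holds as a matter of precision and prespecification, not of validity. The plan balances a factor unrelated to its primary outcome and leaves the collected baseline count out of both the allocation and any named primary model.

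Under the assumptions of 10% to 30% capped men and a gap of 20 to 40 million, about 6% to 58% of the planned variance is explainable. The standard error at 117 per arm would then fall from 3.14 to between 3.04 and 2.03 million. So wide a range means that the benefit could be slight or large. The route mix, the gap, the baseline correlation and the use of 38 million for the whole population are all assumed. The trial's own baseline data would settle the mix.

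**What to change.** In Data Analysis, prespecify the primary analysis as a linear model, on a suitable transformed scale, of retrieval-day total motile sperm on arm, adjusting for baseline unprocessed total motile sperm and the PGT-A stratum. This is the essential change: stratified blocks followed by an unadjusted test recover only part of the gain.

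In Randomization, if it has not started, keep PGT-A and add baseline unprocessed total motile sperm (<10 v ≥10 million, the threshold already among the entry criteria) as a second stratifier. Eligibility rests on two analyses that may straddle the threshold, so state which sample counts, for example the most recent. The value is known in time, since randomization takes place on stimulation day 6 to 8. If enrolment has begun, the covariate alone recovers most of the benefit.

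The cost is one more randomization field, four strata instead of two (workable with 234 men) and slightly more analysis work. No extra patients are needed.

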### **B. Statistical Considerations**

# **Sample Size Justification**

Our sample size calculation is based on data from Boston IVF from 2013 to 2018 for patients with less

than 3 million total motile sperm post prep for IVF/ICSI patients. The mean number of total motile sperm is 38 million  $\pm$  24 which will be our control group. We hypothesize that the mean number of total motile sperm at the time of retrieval will increase to 48 million. In order to achieve 80% power to detect the specified difference using a two-sided alpha of 0.05, we will need 90 evaluable participants per arm. We anticipate that approximately 15% of participants will drop out or crossover, and we will inflate the sample size by another 15% to account for a non-normal distribution. Thus, we aim to randomize 117 participants per arm for a total of 234 participants.

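### Does planning on an SD of 24 million from one subgroup of clinic patients leave the trial's 80% power unsupported?

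*Combined protocol and SAP*

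**What the plan says.** The Sample Size Justification uses records of the trial's own clinic, 2013 to 2018, restricted to men whose processed count fell under a cut-off. The text reads "than 3 million total motile sperm post prep for IVF/ICSI patients. The mean number of total motile sperm is 38 million", followed by a spread of 24, and adopts this as the control group. The alternative is given as "We hypothesize that the mean number of total motile sperm at the time of retrieval will increase to 48 million". For "80% power to detect the specified difference using a two-sided alpha of 0.05", the section states that "we will need 90 evaluable participants per arm". It then adds 15% for dropout or crossover and another 15% for non-normality, reaching 117 per arm and 234 in total.

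The Inclusion Criteria are wider than the planning group. A man qualifies with "at least 1 of the following on 2 semen analysis with at least one being in the past 12 months". The list contains a concentration limit of 10 million/mL, a motile-count criterion ("unprocessed semen analysis with < 10 million motile sperm or processed semen analysis with < 3 million motile sperm"), and morphology below 2% normal forms, which sets no limit on count.

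On the outcome, Methods says "The semen sample provided on day of oocyte retrieval will be analyzed with a basic and advanced semen panel". On abstinence in current practice, it says "Counseling on EA varies among the medical care teams at Boston IVF as some patients may or may not receive explicit EA instructions". Data Analysis leaves the choice between a parametric and a non-parametric test for continuous variables to the observed distribution.

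**The concern.** Three features make the planning figure look insecure.

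First, it comes from men who fit one half of one criterion (processed count below 3 million), while the trial also admits men on concentration, unprocessed count or morphology. Their spread may differ.

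Second, the figure is hard to place. A mean of 38 million cannot be the same post-prep measurement that selected men for being below 3 million, so it must come from another specimen or occasion, and none is named. If it is the raw ejaculate, mean recovery in that group is below 3/38 = 7.9%, whereas the paired cut-offs in the Inclusion Criteria imply 3/10 = 30%. The timing of the control figure is not given either; only the hypothesised 48 million is tied to retrieval.

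Third, the figure stands for the arm abstaining more than 48 hours, yet abstinence advice at the clinic was not uniform.

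In a two-sample t-test with a fixed 10-million difference and fixed n, the SD determines power. If the SD were well above 24 million, a null result would be hard to interpret, and nothing in the plan would reveal this before the final analysis.

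**Working it through.** **Inputs (Sample Size Justification).** Difference 48 − 38 = 10 million; SD 24 million (the ± is not labelled, but reading it as an SD reproduces the stated n); two-sided alpha 0.05; power 80%; 90 evaluable and 117 randomised per arm.

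**Reproducing the plan.** Normal approximation:

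n per arm = 2 × (1.96 + 0.84)² × (24/10)² = 90.4, rounded up to 91.

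The t-test version gives 91.4, rounded up to 92. Power at 90 per arm is 79.8% (normal) or 79.4% (t-test). The inflation is additive: 90 × (1 + 0.15 + 0.15) = 117. Compounding would give 90 × 1.15² = 119.0. The stated figures hold to within rounding.

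**Sensitivity to the SD.** Every SD other than 24 is an assumption, because the document gives no other. Two-sided t-test, difference 10 million:

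| SD (million) | 90 per arm | 99 per arm | 117 per arm |
|---|---|---|---|
| 19 | 94% | 96% | 98% |
| 24 | 79% | 83% | 89% |
| 27 | 70% | 74% | 81% |
| 30 | 60% | 65% | 72% |

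The 99 is 117 × 0.85 = 99.45, the number left after the planned loss, with the non-normality allowance counted as ordinary sample. The 117 column is an upper bound: everyone supplies a sample and crossover does not dilute the effect. By the normal approximation, the largest SD that keeps 80% power is 10 × √(n/2)/(1.96 + 0.84): 23.9 at 90, 25.1 at 99 and 27.3 at 117.

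**Is the SD alone decisive?** Not under this plan, which allows a rank test. Log-normal data were simulated with control mean 38, SD 30 and 90 per arm (4,000 runs):

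- An additive shift of 10 million gives about 62% power by t-test and 92% to 93% by Mann-Whitney.
- A multiplicative effect (38 to 48) gives about 51% to 52% by t-test and 58% to 59% by Mann-Whitney.

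Power therefore depends on the form of the effect and the test as well as on the SD. The normal-data rows at large SDs also need care: with mean 38 and SD 30, a normal model puts 10% of men below zero motile sperm.

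**What a blinded re-estimation rule would cost.** Consider a rule that computes the pooled SD from the first 90 retrieval-day values and sets n per arm to the larger of 90 and 2 × (1.96 + 0.84)² × (SD/10)² + 1. In simulation, with normal and log-normal data and a final t-test:

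- SD 30: power rises from 61–62% to 80%, with a mean of 146.5 to 147.7 evaluable per arm. Multiplied by 1.30, that is 190 to 192 randomised per arm against 117.
- SD 24 (the plan is right): power goes from 79–80% to 82–85%, with a mean of 99.1 to 104.3 evaluable. Multiplied by 1.30, that is 129 to 136 randomised per arm, 10% to 16% above plan.
- SD 19: about 94% either way, with 90 to 91 evaluable.

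Type I error stays at 4.6% to 5.0%.

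**The case for a change.** The strongest case for acting is that the gap is real and a check is cheap to write. The two 15% allowances are assigned to loss and to non-normality, not to a wrong SD. Even if the second is treated as spare, an SD of 30, only 25% above plan, leaves 65% power. The outcome is known on retrieval day, so a pooled SD could be computed during enrolment without arm information, and the simulated type I error is sound. If the SD is small, almost nothing is spent.

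Much of this stands. The source details are missing, the planning group is narrower than the enrolled group, and blinded re-estimation would work as described.

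What does not stand is the step from undocumented to deficient. The direction of any error is open: the unprocessed-count route caps the count on the qualifying sample, which could make the spread smaller, while the morphology route has no cap. The comparison of 7.9% with 30% sets a group mean against two alternative eligibility thresholds that need not be equivalent, so it shows no error. A mean above the entry cut-offs is not a contradiction either, since the qualifying samples and the retrieval-day sample are different occasions. The rule itself is one-sided: it raises enrolment even when 24 is right, and by using only the SD it could add participants without need if a rank test is used on skewed data.

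**Conclusion.** No change is needed. The plan delivers what it states: about 91 to 92 evaluable per arm against 90, and 79% to 80% power, given a 10-million difference and an SD of 24 million. Whether that SD holds for the enrolled men cannot be settled from the document in either direction, so no power shortfall is shown. The illustrative range at 90 per arm, from 94% (SD 19) to 60% (SD 30), rests on assumed SDs and a t-test.

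The unnamed specimen, timing and abstinence behind 38 ± 24 are a documentation gap. Filling it would help a reader but would not alter enrolment, conduct or analysis. A blinded SD check is a fair design option. Leaving it out trades protection against a large SD for a fixed sample of 234, against about 380 to 384 if the SD were 30. The final confidence interval will show the precision achieved in either case.

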# **Data Analysis**

We will conduct both intention-to-treat and per-protocol analysis. Both intention-to-treat and per-protocol analyses are noted in the RCT reporting guidelines (CONSORT) as valid approaches. For this study, we will perform an intention-to-treat analysis because it is the gold standard for RCTs, even with crossover or withdraw. We also will perform a per-protocol analysis. While this analysis can introduce bias, it is a valid statistical approach.

Descriptive data will be presented as a proportion, mean with standard deviation or median with interquartile range. Comparisons will be made using Chi-square or Fisher's exact test for categorical variables and parametric or non-parametric tests for continuous variables based on data distribution. Log-binomial regression will be used to estimate risk ratios and 95% confidence intervals for the primary and secondary outcomes. While we anticipate that randomization will balance the distribution of measured and unmeasured potential confounders in the two study arms, if this is not the case, we will assess the influence of potential confounders as needed. All data will be analyzed with SAS 9.4 (SAS Institute Inc., Cary, NC, USA). All tests will be two sided and a P value <0.05 will be required to confer significance.

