#### Consent

We are requesting a HIPAA waiver for pre-screening and recruitment. For the study intervention, we are requesting a waiver of documentation of consent. Participants will be informed in the recruitment

email the study is completely voluntary. The day following the recruitment email, eligible participants will receive a phone call from a member of the research team to discuss the study and obtain verbal consent if the eligible participant is interested in participating in the study (see verbal consent). If the participant does not answer, a voicemail will be recorded followed by a second phone call the following day. The recruitment and consent process will occur between the pre-IVF period and before stimulation day 4 of the IVF cycle. If a participant consents to enrollment, we will make a note in the treatment plan for their IVF cycle. Throughout the study, we will let participants know that they have the option to stop participating at any time and that their care would not be affected by that decision.

We anticipate that a proportion of participants may desire to crossover to the other assigned EA period. If this occurs, participants will be instructed to email or call the research team. These patients would be included in the per protocol analysis. The study team will access the patients' medical records for up to 24 months following randomization in order to follow the clinical/pregnancy outcomes. These outcomes are recorded as part of routine clinical care.

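### The stated 80% power makes no allowance for crossovers diluting the intention-to-treat difference; they are only replaced by headcount

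*Combined protocol and SAP*

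**What the plan says.** The Sample Size Justification (B3, section B) takes a control mean of 38 million, an SD of 24 million and an expected mean of 48 million under short abstinence. The calculation is set up as "In order to achieve 80% power to detect the specified difference", "using a two-sided alpha of 0.05", and concludes that "we will need 90 evaluable participants per arm". Losses are then handled in one sentence: "We anticipate that approximately 15% of participants will drop out or crossover, and we will inflate the sample size by another 15" per cent for a non-normal distribution. The target is 117 randomized per arm, 234 in total. The 15% is not divided between dropout and crossover, and the 10 million difference is not reduced.

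Other sections say what happens to crossovers:

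- Methods: "Participants who crossover to the alternate treatment arm will continue their participation in the study so that we can collect cycle outcome data".
- Randomization: the plan expects that most "crossovers will occur due to participants wishing to be in the alternate EA period or not being able to produce a sample" in the assigned window.
- Data Analysis: "we will perform an intention-to-treat analysis because it is the gold standard for RCTs, even with crossover or withdraw". A per-protocol analysis is also planned.
- Consent (B6), on participants who cross over: "These patients would be included in the per protocol analysis".

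**The concern.** Dropout and crossover damage a trial in different ways. A dropout removes an observation, and one more recruit replaces it. A crossover supplies an observation, but under the other arm's abstinence. Analysed as randomized, it pulls the two arm means together. Power then falls through the difference itself. To offset a proportional loss s in the difference, the sample must grow by 1/(1 − s)², not by a simple headcount factor. For s = 0.15 that is 1/0.85² = 1.38, against the 1.15 allowed.

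The headcount approach would suit an analysis that leaves crossovers out. The Consent section says they are included in the per-protocol analysis, so neither described analysis clearly removes them.

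What is at stake is how a null result is read. A reader would set a non-significant intention-to-treat result against a stated 20% chance of missing a true 10 million difference. If 5 to 7.5% cross over in each arm, that chance is about 24 to 34%. The plan itself foresees crossover from preference and from missed windows, so some dilution is expected.

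**Working it through.** **Inputs from the plan.** Difference 48 − 38 = 10 million; SD 24 million (the figure after ±, read as an SD); two-sided alpha 0.05; power 80%; 1:1 allocation; 90 evaluable and 117 randomized per arm; 15% pooled dropout or crossover; another 15% for non-normality.

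**Reproducing the plan's figures.** The two-sample t-test needs 91.4 per arm for 80% power, and the normal approximation gives 91. Power at 90 per arm is 79.4% (t-test). The base of 90 is therefore right to within rounding. Also 90 × (1 + 0.15 + 0.15) = 117 exactly, which confirms that both allowances are pure headcount at the undiluted difference.

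**Adding dilution.** Let d be dropout in each arm, and c_short and c_long the crossover rates in the two arms, all as shares of those randomized.

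- Crossover among those measured: c′ = c/(1 − d)
- Intention-to-treat difference: 10 × (1 − c′_short − c′_long)
- Sample per arm: n = 117 × (1 − d)/k

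Here k = 1.15 treats the non-normality allowance as spent on its stated purpose, and k = 1 counts it all as usable sample. Worked example, d = 0.10 and c = 0.05 in each arm: c′ = 0.05/0.90 = 0.0556; difference = 10 × (1 − 0.1111) = 8.89; n = 105.3/1.15 = 91.6, or 105.3 unspent; power 0.703, or 0.763.

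| Dropout (both arms) | Crossover | Difference (million) | n per arm, spent (unspent) | Power, spent (unspent) |
|---|---|---|---|---|
| 15% | none | 10.00 | 86.5 (99.5) | 0.778 (0.832) |
| 10% | 5% each arm | 8.89 | 91.6 (105.3) | 0.703 (0.763) |
| 7.5% | 7.5% each arm | 8.38 | 94.1 (108.2) | 0.664 (0.725) |
| 7.5% | 7.5% one arm only | 9.19 | 94.1 (108.2) | 0.743 (0.801) |
| 7.5% | 7.5% each arm, half effect | 9.19 | 94.1 (108.2) | 0.743 (0.801) |
| 0 | 15% one arm only | 8.50 | 101.7 (117) | 0.710 (0.770) |
| 0 | 15% each arm (extreme) | 7.00 | 101.7 (117) | 0.544 (0.603) |

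All rows except the half-effect one assume that a crossover takes on the other arm's full mean. The half-effect row stands for someone landing between 24 and 48 hours. Reading c directly as a share of those measured raises the mixed full-effect cases by about one point. Mixing raises the SD to at most 24.3, which is ignored.

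**How much crossover the 80% can bear.** This is the largest c′_short + c′_long that keeps 80% power at full effect, with the difference detectable at 80%:

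| Dropout | Max. summed crossover, spent (unspent) | Detectable difference (million), spent (unspent) |
|---|---|---|
| 0 | 5.3% (11.7%) | 9.47 (8.83) |
| 7.5% | 1.5% (8.2%) | 9.85 (9.18) |
| 10% | 0.1% (6.9%) | 9.99 (9.31) |
| 15% | none (4.2%) | 10.28 (9.58) |

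**A minor point.** Adding the two allowances gives 117. Compounding them gives 90 × 1.15 × 1.15 = 119.0 or 90 × 1.15/0.85 = 121.8. With all 15% as dropout and the allowance spent, power is 0.778 at 117 and 0.795 at 122. That is about two points and would not merit a comment alone.

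**The case against.** The best reply is that the plan ties its 80% to evaluable participants and never names intention-to-treat as primary. On that reading, the 90 are adherent completers, dropouts and crossovers are added on top, and the sizing is coherent for a per-protocol comparison. Part of this stands: the stated figures do reproduce, and the fault is a missing planning term, not a slip in multiplication. But the term evaluable is not defined, the Data Analysis section justifies intention-to-treat explicitly in the presence of crossover, and the Consent section puts crossovers into the per-protocol analysis. That crossovers stay in their randomized arm is not spelled out, but it is the ordinary meaning of intention-to-treat.

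A second reply is that the size of the loss rests on figures the documents do not contain: the split, the direction of crossover and the mean among crossovers. That is true. One-way crossover of 7.5%, or two-way crossover at half effect, leaves 80% if the whole non-normality allowance counts as sample, and 74% if it does not.

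A third is that the allowance-spent column starts at 78% with no crossover at all, so not every point below 80% is dilution. That also stands. Against their own no-crossover baselines, the cases with 5% crossover in each arm lose about 7 points (0.778 to 0.703, and 0.832 to 0.763). Nor does the plan say exactly what the non-normality allowance buys, which is why both columns are given.

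**Conclusion.** The concern holds. The sample-size paragraph has no dilution term, while the analysis that the plan calls the gold standard retains crossovers, so an unconditional 80% is not supported for intention-to-treat. That conclusion is firm; its size is conditional. With crossover of 5 to 7.5% in each arm, the rest of the 15% being dropout, and the full effect carried over, power is about 66 to 76%. In milder cases (one arm only, or half effect) it is about 74 to 80%. If the whole 15% is dropout, there is no dilution and power is 78 to 83%. The claim survives only when crossover is small, or when it is modest and the non-normality allowance is left wholly available. This should be fixed, but it does not undermine the design.

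**What to change.** Keep 234 participants and rewrite the sample-size paragraph:

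1. State expected dropout and per-arm crossover separately, as shares of those randomized.
2. Report intention-to-treat power over a plausible range of these rates, using the formulas above, with and without the 1.15 factor. Put that range in place of the single 80%.
3. Give the intention-to-treat difference detectable with 80% power: about 9.5 million with no dropout and 10.3 million with 15% dropout if the non-normality allowance is spent, or 8.8 and 9.6 million if it is not.

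It would also help to name the primary analysis and to reconcile the Consent section's statement on crossovers with the per-protocol analysis, so that the restated power clearly belongs to the primary test.

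The cost is rewording and, under most splits, a less favourable power figure. Enrolment and conduct do not change.
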